**Table 8. Dose Modification and Management of immune-related AEs**

Document Name: GCT1021-01 Protocol

Document Number: TMF-03326

Version: 11.0

Immune-related AEs	Toxicity grade (CTCAE v4.03)	Dose Modification	Guidance for Management of Immune-related AEs
Hepatitis (Elevated Liver Function Tests [LFTs]) Infliximab should not be used for management of Immune Related Hepatitis	Any Grade	-	
 
- Monitor and evaluate liver function test: AST, ALT, ALP, and TB.
 
- Evaluate for alternative etiologies (e.g., viral hepatitis, disease progression, concomitant medications).
 

	Grade 1 (AST or ALT > ULN to 3 x ULN and/or total bilirubin (TB) > ULN to 1.5 x ULN)	No dose modification If it worsens to Grade 2, refer to guidance for treatment of Grade 2 event	For Grade 1 AST or ALT and/or TB elevation: 
 
- Continue LFT monitoring per protocol.
 

	Grade 2 (AST or ALT > 3 to 5 x ULN or TB > 1.5-3.0 x ULN)	Hold trial drug resolution to ≤ Grade 1 
 
• If toxicity worsens to Grade 3 or 4, refer to guidance for treatment of Grade 3 or Grade 4 event
 
• If improves to baseline, then treat at next scheduled treatment date
 
	For Grade 2 AST or ALT and or TB elevation: 
 
- Regular and frequent checking of LFTs (e.g., every 1-2 days) until elevations of these are improving or resolved.
 
- If no resolution to ≤ Grade 1 in 1-2 days, discuss with study physician.
 
- If event is persistent (> 3-5 days or worsens, promptly start prednisone 1-2 mg/kg/day or IV equivalent.
 
- If still no improvement within 3-5 days despite 1-2 mg/kg/day of prednisone or IV equivalent, consider additional workup and prompt treatment with IV methylprednisolone 2-4 mg/kg/day started.
 
- If still no improvement within 3-5 days 2-4 mg/kg/day despite IV methylprednisolone, promptly start immunosuppressive (mycophenolate mofetil at 500 mg every 12 hours). Discuss with study physician if mycophenolate mofetil is not available. Infliximab should not be used.
 
- Once improving, gradually taper steroids over > 4 weeks and consider prophylactic antibiotics, antifungals and anti PPCP treatment (please refer to current NCCN guidelines for treatment of cancer related infections [Category 2B recommendations]).
 

Template No.: 07-072

Template version: 0.1

Template Date: 03 Feb 2014

Document Name: GCT1021-01 Protocol

Document Number: TMF-03326

Version: 11.0

	
Grade 3 (AST or ALT > 5 - 20 x ULN and /or TB > 3.0-10 x ULN
	
For elevations in transaminases ≤ 8 x ULN, or elevations in bilirubin ≤ 5 x ULN
 
 
- Hold trial drug until resolution to ≤ Grade 1 or baseline
 
- Resume trial drug administration at the next scheduled dose if elevations resolve to ≤ Grade 1 or baseline within 14 days
 
 
Permanently discontinue trial drug/ if the elevations do not resolve to ≤ Grade 1 or baseline within 14 days.
 
For elevations in transaminases > 8 x ULN or elevations in bilirubin > 5 x ULN, permanently discontinue trial drug.
 
Permanently discontinue trial drug for any case meeting Hy's law criteria (ALT > 3 x ULN + bilirubin > 2 x ULN without initial findings of cholestasis (i.e., elevated alkaline P04) and in the absence of any alternative
	
For Grade 3 or 4 AST or ALT and/or TB elevation:
 
 
- Promptly initiate empiric IV methylprednisolone at 1 to 4 mg/kg/day or equivalent.
 
- If still no improvement within 3 – 5 days despite 1 to 4 mg/kg/day methylprednisolone IV or equivalent, promptly start treatment with immunosuppressive therapy (mycophenolate mofetil at 500 mg every 12 hours). Discuss with study physician if mycophenolate is not available. Infliximab should not be used.
 
- Hepatology consult, abdominal workup, and imaging as appropriate.
 
- Once improving, gradually taper steroids over ≥ 4 weeks and consider prophylactic antibiotics, antifungals and anti PCP treatment (please refer to current NCCN guidelines for treatment of cancer related infections [Category 2B recommendations]).
 

--	---	---	--

Template No.: 07-072

Template version: 0.1

Template Date: 03 Feb 2014

Document Name: GCT1021-01 Protocol

Document Number: TMF-03326

Version: 11.0

		cause	
	Grade 4 (AST or ALT > 20 x ULN and/or TB > 10 x ULN)	Permanently discontinue trial drug	
Pneumonitis	Grade 1-2	1st occurrence If there is radiographic evidence of pneumonitis progression, hold treatment until there is evidence of improvement/resolution to Grade 1 or less  2nd occurrence Permanently discontinue	Monitor for signs and symptoms of pneumonitis. Evaluate for pneumonitis with radiographic imaging. For $\geq$ Grade 2: Consider initiation of corticosteroid treatment (initial dose of 1-2 mg/kg prednisone or equivalent followed by taper). Corticosteroid taper should be initiated when the immune-related AE improves to $\leq$ Grade 1.
	Grade 3 or 4	Permanently discontinue	
Colitis	Grade 2	Continue treatment at the discretion of the investigator	Monitor for signs and symptoms of colitis. Consider gastroenterology consultation and confirm diagnosis of colitis. Consider administration of corticosteroids (initial dose of 1-2 mg/kg prednisone or equivalent) followed by taper. Corticosteroid taper should be initiated when the immune-related AE improves to $\leq$ Grade 1.
	Grade 3	Refer to text below	
	Grade 4	Permanently discontinue	
Type 1 diabetes mellitus (T1DM) or Hyperglycemia	Newly diagnosed T1DM or Grade 3-4 hyperglycemia	Refer to text below	Monitor for hyperglycemia or other signs and symptoms of diabetes. Consider endocrinology consultation. Consider administration of insulin for type 1 diabetes. Consider administration of anti-hyperglycemic in subjects with hyperglycemia.
Hypophysitis	Grade 2	Continue treatment at the discretion of the investigator	Monitor for signs and symptoms of hypophysitis. Consider endocrinology consultation. Consider administration of corticosteroids and initiate hormonal replacements as clinically indicated. Corticosteroid taper should be initiated upon immune-related AE improving to Grade 1 or less.
	Grade 3 or 4	Refer to text below	

Document Name: GCT1021-01 Protocol

Document Number: TMF-03326

Version: 11.0

Hyperthyroidism	Grade 2	Continue treatment at the discretion of the investigator	Monitor for signs and symptoms of thyroid disorders. Consider management with thionamides and beta-blockers as appropriate.
	Grade 3-4	Refer to text below	
Hypothyroidism	Grade 2	Continue treatment at the discretion of the investigator	Monitor for signs and symptoms of thyroid disorders. Consider endocrinology consultation. Consider initiation of thyroid replacement hormones per standard of care.
	Grade 3-4	Refer to text below	
Nephritis and Renal dysfunction	Grade 1	Consider temporary hold pending consideration of baseline renal function and to confirm etiology 	Monitor for changes in creatinine levels. For $\geq$ Grade 2: If worsening or no improvement, consider administration of corticosteroids (prednisone 1-2 mg/kg or equivalent) followed by taper. Corticosteroid taper should be initiated upon immune-related AE improving to Grade 1 or less.
	Grade 2	Hold treatment until resolved to baseline 	
	Grade 3-4	Permanently discontinue	
Skin Toxicities	Grade 1-2	Continue treatment at the discretion of the investigator	Based on the severity of the adverse reaction, consider administration of corticosteroids. Corticosteroid taper should be initiated upon immune-related AE improving to Grade 1 or less.  For signs or symptoms of Steven Johnsons Syndrome (SJS) or Toxic Epidermal Necrolysis (TEN), withhold and refer the subjects for specialized care. If SJS or TEN is confirmed, permanently discontinue.
	Grade 3	Refer to text below	
	Grade 4	Permanently discontinue	
All other immune-related AEs	Grade 2	Continue treatment at the discretion of the investigator	Based on type and severity of AE, consider administration of corticosteroids. Permanently discontinue for any Grade 3 immune-related AE that recurs and for any life-threatening immune-related AEs.
	Grade 3	Refer to text below or discontinue based on the type of event.	
	Grade 4	Permanently discontinue	

1 20

Document Name: GCT1021-01 Protocol

Document Number: TMF-03326

Version: 11.0

---

[Redacted text block]

[Redacted text block]

[Redacted text block]

Document Name: GCT1021-01 Protocol

Document Number: TMF-03326

Version: 11.0

**Dose Delays**1Q3W and 3Q4W Schedule

For immune-related AEs, please refer to Section 7.3.3 regarding dose delays.

For all other AEs/Toxicities, enapotamab vedotin administration can be delayed for up to a maximum of 12 weeks. Radiological assessments should be continued during this period, as per protocol Section 8.4.7 and as clinically indicated, to monitor for disease progression.

Patients should be withdrawn from treatment if the treatment delay exceeds 12 weeks or if disease progression is observed while treatment is interrupted.

3Q4W Schedule Only

If a patient has to delay a dose for more than 14 days and the toxicity has resolved by that time, the patient should start with a new regular cycle upon resuming treatment.

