**Table 3. Dose Modification for enapotamab vedotin related Non-Hematologic toxicity occurring during a cycle**

Non-Hematologic Toxicity	Enapotamab Vedotin Dose Modification
Thrombosis/embolism $\geq$ Grade 2	If the event occurred without or during inadequate anticoagulation, initiate adequate anticoagulation treatment. Enapotamab vedotin dosing may continue without interruption at the discretion of the treating physician. Dose level may be maintained at the discretion of the treating physician.  If the event occurred during adequate anticoagulation treatment (prophylactic dose of anticoagulation therapy with LMW heparin, heparin or Coumadin), discontinue enapotamab vedotin.
Peripheral Neuropathy = Grade 1 (only worsening from G0 to G1)	Enapotamab vedotin dosing should be reduced to a lower dose level as indicated in Table 5 , Table 6 and Table 7 without dose interruption.
Peripheral Neuropathy = Grade 2 or 3	Enapotamab vedotin dosing should be interrupted. Decrease dose (as indicated in Table 5 , Table 6 or Table 7 depending on dose and schedule (neuropathy must resolve to $\leq$ Grade 1).
Peripheral Neuropathy = Grade 4	Permanently discontinue enapotamab vedotin.
Other enapotamab vedotin related AEs $\geq$ Grade 3	Enapotamab vedotin dosing should be interrupted. Decrease by one dose level when dosing is resumed (see Table 4 , Table 6 and Table 7 ) (AEs must resolve to $\leq$ Grade 2).

For AEs and grades not addressed above, any dose modification must be discussed with the medical monitor.

Document Name: GCT1021-01 Protocol

Document Number: TMF-03326

Version: 11.0

In case dose reduction is required due to AE as per protocol (see [Table 2](#), [Table 3](#) and [Table 8](#)), the dose must be reduced according to the guidelines provided in [Table 4](#) to [Table 7](#) depending on the dose and dosing schedule as follows:

[Redacted]

**Table 4.** [Redacted]

[Redacted]

[Redacted]

**Table 5.** [Redacted]

[Redacted]

[Redacted]

**Table 6.** [Redacted]

[Redacted]

If 1.0 mg/kg dose cannot be tolerated by patient on the 1Q3W schedule (independent of type of AE), enapotamab vedotin should be permanently discontinued.

[Redacted]

Document Name: GCT1021-01 Protocol

Document Number: TMF-03326

Version: 11.0

---

**Table 7.** [REDACTED]

[REDACTED]

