### 7.3.3 Immune-related Adverse Events

Guidance for dose modification and management of immune-related AEs is provided in [Table 8](#). For Grade 1 immune-related AEs, enapotamab vedotin treatment should be continued with close monitoring. Corticosteroids taper should be initiated over the course of at least 4 to 6 weeks when the immune-related AE improves to  $\leq$  Grade 1. Trial treatment should be permanently discontinued for any serious Grade 3 immune-related AE that recurs and for any Grade 4 immune-related AE, with the exception of endocrinopathies that have been controlled by hormone replacement. For additional guidance on the recommended management of immune-related AEs, please refer to the *Management of Immune-Related Adverse Events in Patients Treated with Immune Checkpoint Inhibitor Therapy: American Society of Clinical Oncology Practice Guideline*.

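### Table 8 prints the Hy's law permanent stop only in the Grade 3 hepatitis cell, while the Grade 2 row lets some of the same patients restart

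*Protocol*

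**What the plan says.** Table 8 gives dose-modification rules for immune-related hepatitis by grade.

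- **Any Grade row.** The management column asks sites to "Monitor and evaluate liver function test: AST, ALT, ALP, and TB" and to look for other causes. The dose-modification cell holds only a dash.
- **Grade 2 row** (AST or ALT above 3x to 5x ULN, or bilirubin above 1.5x to 3x ULN). The drug is held. Two instructions follow: "If toxicity worsens to Grade 3 or 4, refer to guidance for treatment of Grade 3 or Grade 4 event" and "If improves to baseline, then treat at next scheduled treatment date". The management column adds a discussion with the study physician if the event has not resolved to Grade 1 or less within 1-2 days. Hy's law is not mentioned.
- **Grade 3 row** (AST or ALT above 5x to 20x, and/or bilirubin above 3x to 10x ULN). The cell sets out hold, resume and stop rules by size of elevation. It then adds "Permanently discontinue trial drug for any case meeting Hy's law criteria", defined as ALT above 3x with bilirubin above 2x ULN, without initial cholestasis or an alternative cause.
- **Grade 4 row.** Permanent discontinuation.

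The opening text of Section 7.3.3 says treatment should be "permanently discontinued for any serious Grade 3 immune-related AE that recurs and for any Grade 4 immune-related AE", apart from hormone-controlled endocrinopathies. The Dose Delays text after the table says: "For immune-related AEs, please refer to Section 7.3.3 regarding dose delays".

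**The concern.** The stop is worded for every Hy's law case, but it is printed where only a reader dealing with a Grade 3 event will look. Its limits (3x and 2x ULN) lie below the Grade 3 cut-points (5x and 3x ULN), so some cases that meet it are Grade 2. For those patients the row matching their grade allows re-treatment on recovery, while the sentence one row down forbids it. A site working from the matching row could re-expose a patient whom the sponsor's own rule removes permanently.

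The issue is patient handling only. The SAP (Section 17.5, and Section 3.8 of the addendum) counts ALT and/or AST above 3x with bilirubin above 2x ULN directly from laboratory values without regard to grade, so no analysis changes.

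**Working it through.** The plan gives no figure to reproduce. The check intersects the Hy's law limits with each hepatitis grade band and reads the instruction printed there.

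**Inputs, all from Table 8 (multiples of ULN)**
- Hy's law: ALT > 3 and bilirubin > 2, plus the two qualifiers.
- Grade boundaries for ALT/AST: 3, 5, 20. For bilirubin: 1.5, 3, 10.
- A patient's grade is the higher of the two test grades.

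**Intersection by grade**

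| Grade | Overlap with the Hy's law limits | Instruction in that row |
|---|---|---|
| 1 | None (ALT at most 3) | No dose modification |
| 2 | ALT > 3 to 5 with bilirubin > 2 to 3 | Hold, then treat at baseline; no Hy's law stop |
| 3 | Yes | Hy's law stop printed |
| 4 | Yes | Permanent stop already ordered |

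Grade 2 is the only row whose own instruction contradicts the stop.

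**Worked case.** ALT 4x (Grade 2, between 3 and 5) and bilirubin 2.5x (Grade 2, between 1.5 and 3) give Grade 2 overall. Since 4 > 3 and 2.5 > 2, the Hy's law limits are met. With no initial cholestasis and no other cause, the Grade 2 row says restart at baseline and the Grade 3 cell says never restart.

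**Grid count (0.1 steps, ALT 3.1-25.0, bilirubin 2.1-12.0)**
- Total: 220 × 100 = 22,000 points, all within the Hy's law limits.
- Grade 2: 20 × 10 = 200.
- Grade 4: 50 × 100 + 170 × 20 = 5,000 + 3,400 = 8,400.
- Grade 3: 22,000 − 200 − 8,400 = 13,400.

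**Share of the Grade 2 band**
- Both tests Grade 2: 20 × 15 = 300 points, of which 200 (67%) meet the limits. This equals (3 − 2)/(3 − 1.5) = 2/3, because the Grade 2 ALT floor is also the Hy's law ALT limit, so bilirubin above 2x alone decides.
- Either test Grade 2, neither higher: 50 × 30 − 30 × 15 = 1,050 points, of which 200 (19%) meet the limits.

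These are shares of a range of values, not of patients.

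**Does other visible text settle it?**
- The opening of Section 7.3.3 supplies no Hy's law stop, and the Dose Delays text only refers back to that section.
- Three steps might catch the patient: the Grade 2 instruction that, without resolution to Grade 1 or less, sites should "in 1-2 days, discuss with study physician"; the line below Table 3, "For AEs and grades not addressed above, any dose modification must be discussed with the medical monitor", if it is read to apply here; and withdrawal by investigator or sponsor decision under Section 6.3.1. Each is a discussion or a discretionary decision, and the first does not arise if values resolve quickly.
- Redacted text follows Table 8 and cannot be checked. Seven cells for other toxicities point to text below the table; no hepatitis cell does.

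**The case against.** The strongest reply is that the protocol already answers the question. The stop carries no grade limit, and its limits sit below the Grade 3 cut-points, so it cannot sensibly mean Grade 3 only. A specific mandatory stop beside a general hold-and-resume rule reads as an exception, and the Grade 3 cell itself is built that way. On this view the fault is one of placement. The literal reading is right, and the rule is not missing. But nothing in the Grade 2 row tells the investigator that the exception exists, and its only pointer to the Grade 3 guidance requires worsening.

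Other points on that side:

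- The opening list in Section 7.3.3 is not exhaustive: Table 8 also orders permanent discontinuation for, among others, a second Grade 1-2 pneumonitis and Grade 3 nephritis. This stands. The introduction's silence is not evidence against the stop; it simply does not provide it.
- Section 7.3.3 refers sites to an external practice guideline for additional guidance, and the redacted blocks might address liver events. Neither can be checked here. They limit any claim that nothing in the section resolves the matter, but the contradictory restart instruction is in plain view.
- The 67% figure conditions on both tests being Grade 2; over the whole Grade 2 region the share is 19%. Both are correct for what they describe.
- The practical risk is small: dosing is already held, and local ALT, AST and bilirubin must be reviewed before each dose (Sections 8.5 and 8.5.1). This also stands, but reviewing normalised values before a dose does not itself enforce a permanent stop.

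**Conclusion.** The concern holds. For immune-related hepatitis with ALT above 3x to 5x and bilirubin above 2x to 3x ULN, no initial cholestasis and no other cause, two rows of Table 8 give opposite instructions on restart. No visible mandatory rule reconciles them at the point of use. The table should be corrected.

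The practical size is likely small. The zone is narrow and the drug is held at presentation. Three patients remained on treatment at version 11.0, safety follow-up ended on 12 November 2021, and the SAP addendum (Section 2.1) reports no clinically significant immune-related findings. No endpoint or analysis is affected. The conclusion assumes that grade is the higher of the two test grades and that the redacted text after Table 8 does not extend the stop to Grade 2.

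**What to change.** Move the Hy's law sentence into the dose-modification cell of the hepatitis Any Grade row, where there is now only a dash. Alternatively, add to the Grade 2 row that re-treatment on recovery does not apply if Hy's law criteria are met, in which case the drug is stopped permanently. Leave the Grade 2 return-to-baseline condition for restart unchanged.

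The cost is one sentence moved or added in one table. No visits or tests are added, because the Any Grade row already requires AST, ALT, ALP and bilirubin and a search for other causes. With the trial finished, the value lies in correcting the text for the record and for any protocol that reuses the table.

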**7.4 Limitation in Concomitant Medication****7.4.1 Prophylactic Concomitant Medications**

Constipation ( $\leq$  Grade 3) has been the most frequently reported clinically significant adverse event. The events seem to be treatment-related and dose-dependent. In order to prevent constipation, oral bisacodyl should primarily be administered as prophylactic treatment. If bisacodyl is not available, ducosate sodium for oral administration should be used.

For each cycle, prophylactic treatment should be initiated on Day 5 following the administration of enapotamab vedotin, or earlier if the patient experiences signs or symptoms of constipation before Day 5. Treatment should continue until Day 21 for the 1Q3W dose schedule and until Day 28 for the 3Q4W dose schedule, with dose adjustments as required.

The doses to be used are as follows:

	Preferred: Bisacodyl, 5 mg (orally)	Alternative: Ducosate sodium 100 mg (orally)
High dose	2 tablets QD at bedtime	1 capsule TID
Mid dose (starting dose)	1 tablet QD at bedtime	1 capsules BID
Low dose	1 tablet every other day at bedtime	1 capsule QD

The Investigator may adjust the starting dose, taking the patient's medical history and use of concomitant opioid medications into consideration.

The investigator should advise patients how to avoid constipation by a diet high in bulk fiber, fruits and vegetables, adequate fluid intake, if possible physical activity and adequate time for toilet visits.

The patient will be given a patient diary for recording of their stool frequency and consistency and use of prophylactic treatment, and be instructed how to complete it and to bring it to every visit.

The site personnel should record the name of the prophylactic treatment and a high dose, mid dose (which is the dose to start with on day 5 of a cycle) and a low dose in the patient's diary.

Document Name: GCT1021-01 Protocol

Document Number: TMF-03326

Version: 11.0

---

The diary will contain guidance on how to modify the dosing of the prophylactic treatment as needed:

- In case of signs and symptoms of constipation, the patient should increase the dose of the prophylactic treatment to the next dose level, indicated in the patient diary. In case the highest dose level is already in use, the patient should contact the trial site for advice. Patients should also be advised to contact the site if they go for more than 48 hours without bowel movements.
- In case of signs and symptoms of diarrhea, the administration of the prophylactic treatment should be interrupted. When diarrhea has resolved, treatment should be reintroduced at a dose level lower than the previous dose taken prior to the development of diarrhea. In case the previous dose was the lowest dose, then the low dose should be used.

Additional treatments, such as senna, milk of magnesia, magnesium citrate, and lactulose should be administered for  $\geq$  Grade 2 constipation and may be considered for  $\leq$  Grade 1 constipation. If not given as primary prophylactic medication to avoid constipation, docusate sodium or bisacodyl may be given in addition.

Any occurrence of diarrhea or constipation should be recorded as an adverse event. Investigators should assess further patients for any evidence of autonomic neuropathy, e.g. postural hypotension in patients with constipation.

Investigators should assess further patients for any evidence of autonomic neuropathy, e.g. postural hypotension in patients with constipation.

Investigators should pay particular attention to the definition of the NCI CTCAE Grade 3 constipation and may well consider that hospital admission equates to “limiting self-care ADL”.

